The measures targeted are TST, sleep efficiency, REM sleep and WASO. This Table shows data from a pilot cross-over study (median and 25th and 75th percentile) for the sleep variables of interest for 15 study subjects. In order to see the HT group with longer TST than the other groups, we will need a sample size of 50 per group for 80% power to detect a difference of 35 minutes, standard deviation of 70, assuming a 2-sided test and type I error rate of 0.016 to account for multiple testing. Similarly for sleep efficiency, we hypothesize a difference of 2% whereas in a previous study we observed a difference of 10%.³¹ Using the sample size of 50 per group we would be able to detect a difference of 7% with a standard deviation of 15, 2-sided test and type I error rate of 0.016, to account for comparing HT to the 3 control groups. Because the percentages depend upon another time dependent variable, the power is based on REM minutes. Using REM minutes, 50 subjects per group would enable us to detect a 15 minutes difference in REM sleep, assuming a standard deviation of 30, power of 80% and a 2-sided test. For WASO, with an assumed standard deviation of 50, a type 1 error rate of 0.016, a power of 80% and a 2-sided test, a difference of 25 minutes will require 50 subjects in each group, producing a total sample size of 200 subjects.

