8.3.3 Statistical Analysis (Aim 3)

The data analytic plan will follow that established for Aims 1 and 2 using a general linear model and use of the appropriate link function dependent upon outcome. Satisfaction variables are notoriously skewed in distribution and so may need to be dichotomized for analysis. Data analysis will be performed in a blinded fashion with regards to the subject and any group assignment. The analysis of cost will include examination of cost to charge ratio (CCR). Because cost fluctuates over time, the annual cost to charge ratio (obtained from Shriners Headquarters) will be used to calculate and apply CCR to charges pertinent to this study in order to determine if the expense of a 1 hour HT session translates to a change in dollars expended in PACU care, total length of hospital stay and morbidity treatment costs (ex. anxiety/pain/itch/anti-nausea medication expense). Cost-benefit analysis comparing those with HT versus no HT and by group will be conducted. An expert in health cost/economics will be consulted where necessary for the latter analysis.

Unfortunately we have no published data with respect to satisfaction or cost analysis. We will be able to detect an effect size of at least 0.66 with a sample size of 50 per group and accounting for multiple testing, with a 2-sided test, a type 1 error rate of 0.016 and power is 80%. A power of 80% could be maintained with correlations as low as $r=0.20$.

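### Fifty per group does not give the stated 80% power for total sleep time and WASO: at two-sided 0.016 it gives 52% per comparison, and Section 8.3.3 contradicts the claim

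*Combined protocol and SAP*

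**What the plan says.** Section 8.3.1 names four PSG measures for sample size and treats them one by one, each with 50 per group.

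- **TST:** "we will need a sample size of 50 per group for 80% power to detect a difference of 35 minutes, standard deviation of 70". The test is two-sided and the error rate is set at 0.016 as an allowance for multiplicity.
- **Sleep efficiency:** the plan says "we hypothesize a difference of 2% whereas in a previous study we observed a difference of 10" points, then says that 50 per group could "detect a difference of 7% with a standard deviation of 15, 2-sided test and type I error rate of 0.016". The error rate is explained as being there "to account for comparing HT to the 3 control groups". This sentence states no power.
- **REM minutes:** 50 per group would detect a "15 minutes difference in REM sleep, assuming a standard deviation of 30, power of 80% and a 2-sided test". This sentence states no error rate.
- **WASO:** with SD 50, a type I error rate of 0.016, 80% power and a two-sided test, "a difference of 25 minutes will require 50 subjects in each group", which leads to the total of 200.

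Section 8.3.3 (Aim 3) says: "We will be able to detect an effect size of at least 0.66 with a sample size of 50 per group", also two-sided, at 0.016 and with 80% power.

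**The concern.** The TST and WASO targets are each half a standard deviation. Section 8.3.3 says that the same group size, error rate, sidedness and power detect 0.66 of a standard deviation. One design cannot have 80% power for both 0.50 and 0.66, so at least one section is wrong.

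The error matters because the Section 8.3.1 paragraph is where the total of 200 is derived, and it concerns the primary objective. If power is overstated, the chance of missing the targeted difference in a given comparison is understated. A non-significant result could then be given more weight as evidence of no effect than the design supports.

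**Working it through.** **Inputs (Section 8.3.1).** n = 50 per group; two-sided α = 0.016 (three comparisons, 0.05/3 = 0.0167, written as 0.016). Standardized differences d = difference/SD:

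- TST 35/70 = 0.50
- WASO 25/50 = 0.50
- REM 15/30 = 0.50
- Sleep efficiency 7/15 = 0.467

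**Method.** Two-sample t-test, equal groups. Noncentrality δ = d·√(n/2) = 5d for n = 50, on 2n − 2 = 98 degrees of freedom. Power is the probability that a noncentral t with parameter δ exceeds the critical value, which is 2.451 at two-sided 0.016.

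**The plan's own figures.** For d = 0.66 (Section 8.3.3), δ = 3.30 and power is 80.0%, so the Aim 3 statement reproduces. In Section 8.3.2, the nausea and vomiting figure (69% versus 40%, 50 per group, 0.016) reproduces at 70%. The anxiety figure (d = 0.7) gives 85% at 0.016, although the text prints 0.16. The 80% in Section 8.3.1 does not reproduce:

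| Measure | d | δ | Stated | Power at 0.016 | Power at 0.05 | n per group for 80% at 0.016 |
|---|---|---|---|---|---|---|
| TST | 0.50 | 2.50 | 80% at 0.016 | 52.2% | 69.7% | 86 |
| WASO | 0.50 | 2.50 | 80% at 0.016 | 52.2% | 69.7% | 86 |
| REM | 0.50 | 2.50 | 80%, no α | 52.2% | 69.7% | 86 |
| Efficiency | 0.467 | 2.33 | no power, α 0.016 | 45.6% | 63.7% | 99 |

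**Cross-check by normal approximation.** Power for d = 0.50 is Φ(2.50 − 2.409) = Φ(0.091) = 53.6%. The sample size is 2(2.409 + 0.842)²/0.50² = 84.5, so 85 per group, against 86 by the t-test. In total, 4 × 86 = 344 subjects, or 4 × 99 = 396 for efficiency.

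**What 50 per group detects at 80% power (0.66 SD).**

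- TST: 0.66 × 70 = 46.2 minutes
- Efficiency: 0.66 × 15 = 9.9 points
- REM: 0.66 × 30 = 19.8 minutes
- WASO: 0.66 × 50 = 33.0 minutes

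**Other readings tried for d = 0.50, 50 per group.**

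- α = 0.0167 instead of 0.016: 52.8%
- Pairwise contrast using the error term from all four groups (196 df): 52.9%
- Four-group omnibus F, one group shifted: 55.4% at 0.016, 72.1% at 0.05
- Healing Touch against 150 pooled controls: 73.6% at 0.016, 86.2% at 0.05

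None gives 80% with the stated inputs. Pooling at 0.05 exceeds 80%, but it is neither the stated error rate nor the stated comparison with three separate controls.

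**The case against.** **The measures do not all make the same claim.** A reader might infer that the plan states 80% power at 0.016 for all four. It does so only for TST and WASO. REM has no error rate, but falls short of 80% at either 0.016 or 0.05. The efficiency sentence states no power; 80% is at most implied by its opening word (similarly) and the shared group size.

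**Covariates could raise power.** In principle they could. To reach 80%, covariates would need a correlation of about 0.64 with TST. The plan states none, Section 8.3.1 places added covariates in secondary analyses, and Section 4.2 records PSG on a single night, so there is no baseline PSG value to adjust for.

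**52% is not the trial's overall chance of success.** This stands. It applies to one comparison, given a true difference at the planned value. If Healing Touch beat all three controls by 35 minutes, the chance of at least one significant TST comparison would be about 77 to 78%, and of all three about 27 to 28%. The plan does not say which counts as success. With the 60-minute difference in medians in the Section 1.1 pilot table (391 − 331) and SD 70, power would be about 96%. A reader might call the whole trial a coin toss; the documents do not support that.

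**The origin of the error is unknown.** A two-sided 0.10 test gives 79.9% and a paired analysis of 46 gives 80.8%, so a reader might infer that one of these was used. Neither matches the stated inputs, and the documents do not say.

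**The assumed SDs.** Dividing the interquartile ranges in the Section 8.3.1 table by 1.349 gives TST SDs of 103.8 and 80.8, above the assumed 70. It is tempting to conclude that 70 is wrong. But the conversion assumes normality, the quartiles are asymmetric and come from 15 subjects, and the assumed REM SD of 30 lies inside its implied range of 23 to 42. This supports a sensitivity note at most.

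**The 2-point efficiency difference.** Power for 2 points is about 4%, but the plan makes no power claim for 2 points, so this is no false statement. The fault is that 2, 7 and 10 points appear together unreconciled.

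**Conclusion.** The Aim 1 power statement is wrong as written. For TST and WASO, 50 per group at two-sided 0.016 gives 52% power per pairwise comparison, not 80%. The chance of missing the targeted difference in a given comparison is therefore about 48% rather than 20%. Section 8.3.3 is right, and it contradicts Section 8.3.1. REM is short of its stated 80% whichever error rate was meant. Efficiency has 46% power for the difference called detectable, though no explicit power figure is contradicted there.

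These results take the plan's own differences, SDs, group size and error rate, with complete data in equal groups and an unadjusted two-sample comparison. No dropout allowance is stated; missing PSG data would lower power further.

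The error lies in the sample size justification. It does not show that Healing Touch lacks effect or that 200 subjects cannot give a useful answer.

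**What to change.** Keep 200 subjects and replace the Section 8.3.1 power text with wording such as:

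> Fifty subjects per group give 80% power per pairwise comparison, at a two-sided type I error rate of 0.016, for differences of about 46 minutes in TST, 9.9 points in sleep efficiency, 20 minutes in REM and 33 minutes in WASO, assuming SDs of 70, 15, 30 and 50. Power is 52% for 35 minutes TST, 25 minutes WASO and 15 minutes REM, and 46% for 7 points of sleep efficiency.

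This states the REM error rate as 0.016; if 0.05 is intended for REM, say so and give 70% for 15 minutes. Reconcile the hypothesized 2-point efficiency difference with the 7 points used for power.

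Optionally, add a sensitivity note using the pilot-implied TST SDs: about 39% power for 35 minutes at SD 81 and 23% at SD 104, labelled as assuming normality and resting on 15 subjects.

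The cost is wording and a less favourable stated power; no subjects or procedures are added. The rewrite discloses the shortfall and does not remove it. Keeping 80% power for the differences now printed would need about 344 subjects, or 396 to include efficiency. That is a choice for the sponsor.

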Because clinical and pharmacological modulation of postburn sleep disturbance has been largely ineffective,^{32-38,87,88} we explored the utility of HT as a potential sleep intervention. The investigation involved 10 children undergoing burn reconstructive care.³¹ Patients were studied an average of 7.2 ± 2 years postburn. Subjects were randomized to HT versus no HT treatment using a 2 period crossover design. Data revealed that HT had a significant effect on both the quantity and quality of sleep. Total sleep time (TST), sleep efficiency, stage 2 sleep (N2) and number of REM periods were significantly enhanced with HT. The percent of time asleep increased during the first 7 hours, which suggests that HT had an extended effect on the parameters being examined beyond that incurred during the HT procedure. Findings of remarkable HT benefit³¹ provide the impetus for this follow-up confirmation study.

EFFECT OF HEALING TOUCH ON SLEEP

VARIABLE	HEALING TOUCH NIGHT N=10	NON-HEALING TOUCH NIGHT N=10	p-value
Total sleep time	391 (251, 476)	331 (268, 373)	.02
Sleep efficiency	76 (53, 90)	66 (55, 78)	.04
Sleep latency	8.4 (2.8, 34.9)	17.2 (13.5, 48.0)	.20
Awakenings	32 (25, 38)	30 (23, 32)	.42
Wake after sleep onset	99 (46, 210)	107 (53, 194)	.77
REM periods	4.5 (2.0, 5.0)	3.5 (2.0, 4.0)	.03
N1 minutes	26 (21, 32)	28 (18, 30)	.83
N2 minutes	213 (136, 236)	160 (107, 204)	.03
N3 minutes	63 (29, 93)	34 (8, 120)	1.0
REM minutes	83 (62, 91)	60 (40, 86)	.20
N1 % norm	212 (174, 241)	304 (197, 531)	.11
N2 % norm	110 (103, 136)	123 (85, 132)	.23
N3 % norm	67 (44, 110)	49 (31, 125)	.43
REM % norm	95 (82, 101)	86 (47, 116)	.73
Efficiency % norm	80 (56, 94)	69 (58, 83)	.04

Data shown as median (25th, 75th percentile)

Taken together, our extensive prior work characterizes significant dyssomnia following injury. Sleep disturbances are long term in nature with widespread health implications for children recovering from burns. Compared with a normal population, seriously burned patients (both acute and rehab/outpatients) demonstrate significant sleep disturbance manifested by decreased total sleep time, frequent arousals, impaired sleep efficiency, nightmares and deficient stages of 3+4 and REM sleep. The pathophysiology underlying postburn sleep deprivation is clearly multifaceted and has not been fully elucidated. Our investigations have led to breakthrough preliminary findings demonstrating the possible clinical efficacy of HT as a sleep intervention.³¹

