8.3 Primary Study Endpoints

8.3.1 Statistical Analysis (Primary Objective)

The primary treatment endpoint for Aim 1 will be generated from PSG. Group comparisons will be made for total sleep time, sleep efficiency, REM, WASO and spectral analysis of C3/C4 delta waves, using a generalized linear random effects model. Secondary analyses will involve adding appropriate covariates to the

model. Age and gender will be retained. Potential covariates include prior experience with HT, medication usage, frequency of random disturbances (such as parents or other caregivers entering the room, cell phones) and number of prior surgical procedures. The same approach will be used to examine hormones, anesthesia emergence, anxiety, and pain scales (Aim 2), the advantage is that the appropriate link function may be applied and we can account for the repeated nature of the design.

Power Analysis

Variable Median (25 th , 75 th percentile)	Healing Touch night N=15	Non-Healing Touch night N=15	p-value
TST minutes	400 (302, 442)	366 (287, 396)	.09
Sleep efficiency %	80 (61, 90)	78 (56, 82)	.07
WASO minutes	72 (47, 160)	85 (82, 181)	.60
REM minutes	86 (62, 93)	63 (40, 97)	.30

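### Sleep efficiency: the plan hypothesizes a 2-point difference but offers power only for 7 points, and on its own inputs power is about 4% at 2 points and about 46% at 7

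*Combined protocol and SAP*

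**What the plan says.** Section 8.3.1 lists sleep efficiency among the Aim 1 group comparisons, and its Power Analysis names it as one of four targeted measures, with total sleep time (TST), REM sleep and WASO.

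The first calculation is for TST: "we will need a sample size of 50 per group for 80% power to detect a difference of 35 minutes, standard deviation of 70", two-sided, type I error 0.016. The next sentence turns to sleep efficiency: "Similarly for sleep efficiency, we hypothesize a difference of 2% whereas in a previous study we observed a difference of 10" (per cent). Then: "Using the sample size of 50 per group we would be able to detect a difference of 7% with a standard deviation of 15", with "2-sided test and type I error rate of 0.016, to account for comparing HT to the 3 control groups". The sleep-efficiency sentences state no power of their own. The 80% comes from the TST sentence through the opening word *similarly*.

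Both prior differences are absolute percentage points between medians from small crossover studies:

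- The 2 points come from the 15-subject pilot table in 8.3.1: "80 (61, 90) 78 (56, 82) .07".
- The 10 points come from the 10-subject table in 1.1 Background: "76 (53, 90) 66 (55, 78) .04".

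Section 8.3.3 (Aim 3) says that 50 per group at two-sided 0.016 gives 80% power for an effect size of at least 0.66.

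**The concern.** Two adjacent sentences give different differences for the same measure. The hypothesized one has no power attached, and the one said to be detectable is 3.5 times as large (7/2) with no explanation. A reader will take sleep efficiency to be as well supported as the TST sentence claims to be, and will take a non-significant result as informative about the effect the investigators expect. If power at 2 points is very low, that reading is wrong. If power at 7 points is also below 80%, the stated figure is wrong as well, and keeping 7 while deleting the 2 would not repair it.

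**Working it through.** **Inputs, all from 8.3.1.** n = 50 per group; SD σ = 15; two-sided α = 0.016 for each comparison of HT with one control; differences δ = 7 (stated as detectable) and δ = 2 (hypothesized). No dropout allowance appears in the power analysis, so all 50 are taken as evaluable.

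**Formula.** Two-sample t-test with 2n − 2 = 98 degrees of freedom. The standard error is σ√(2/n) = 15 × √(2/50) = 15 × 0.2 = 3.0 points. The noncentrality is δ/3.0. The critical value at 0.016 two-sided is 2.451 (normal: 2.409).

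**1. The plan's own figure, 7 points.** Noncentrality 7/3 = 2.333. Power is 45.6% by noncentral t, or Φ(2.333 − 2.409) = 47.0% by the normal approximation. The implied 80% does not reproduce. It would need 2 × (2.409 + 0.842)² × 15²/7² = 98 per group (99 by exact t).

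Other readings of the same sentence (normal approximation unless marked):

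| Reading, δ = 7, SD 15 | Power |
|---|---|
| α = 0.05/3, two-sided | 47.6% |
| Four-group ANOVA F-test at 0.016 | 47.8% |
| One-sided 0.016 | 57.5% |
| Two-sided 0.05 (exact t) | 63.7% |
| HT v pooled controls (50 v 150), 0.016 | 67.3% |
| One-sided 0.05 | 75.4% |
| 50 pairs, paired formula, 0.016 | 81.4% |
| 50 v 150 at 0.05 | 81.5% |

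Only the last two reach 80%. The paired formula contradicts the parallel-group design. Pooling the controls at 0.05 contradicts the stated α and the stated comparison with three separate controls.

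**2. Difference detectable with 80% power.** (2.409 + 0.842) × 3.0 = 9.75 points; 9.90 by exact t. As an effect size, 9.90/15 = 0.66, the figure in 8.3.3. The plan's Aim 3 statement is therefore correct and shows that 7/15 = 0.47 cannot have 80% power on the same inputs.

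**3. The hypothesized 2 points.** Noncentrality 2/3 = 0.667; power 4.1%. At two-sided 0.05 it is 10.1%, and at one-sided 0.05 it is 16.4%, the highest of the readings tried. With an assumed SD from 10 to 20, power at 0.016 runs from 7.8% down to 3.0%. For 80% power the trial would need 2 × (2.409 + 0.842)² × 15²/2² = 1,189 per group (1,191 by exact t), or an SD of about 3.1 with 50 per group.

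**4. What a result could show.** An observed difference reaches significance only above 2.451 × 3.0 = 7.35 points. That is also the half-width of the matching 98.4% confidence interval. An observed difference of zero gives −7.35 to +7.35, which contains 2. The interval excludes +2 from above only if the observed difference is below 2 − 7.35 = −5.35.

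**5. TST, for comparison.** Noncentrality 35/(70 × 0.2) = 2.5; power 52.2%. REM at 15/30 has the same standardized difference of 0.5, hence the same power if 0.016 applies; the REM sentence states no α.

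**The case against.** The best defence has four parts.

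*Seven points is a detectable difference, not the basis of the sample size.* This stands. The text says 50 per group is needed for TST and for WASO, and for sleep efficiency takes 50 as given. A reader might infer that the trial was sized on 7 points; the wording does not support that. But a detectable difference must still be right at the stated inputs, and 7 is not.

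*Seven lies between the two prior estimates, 2 and 10.* True, and at 10 points power is about 81%. The plan does not offer this as its reason, though, and 10 is not what it hypothesizes.

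*Medians understate the pilot difference.* The pilot's lower and upper quartiles differ by 5 (61 v 56) and 8 (90 v 82). A rough mean, (Q1 + median + Q3)/3, is 77 against 72, a difference of 5. This is an assumption, because the documents give no means. It makes a target above 2 more plausible, but power at 5 points is only about 22% (noncentrality 5/3 = 1.67), and the plan's explicit hypothesis is still 2.

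*Covariate adjustment would reduce the SD.* PSG is recorded on one night only, so there is no baseline sleep efficiency to adjust for. Even covariates correlated 0.7 with the outcome would raise power at 2 points only to about 7%.

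A reader might also extend the point to WASO, since the pilot medians differ by 13 minutes and the plan uses 25. The plan never hypothesizes 13 minutes, and the rough means give 93 against 116, a difference of 23. There is no comparable contradiction there.

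**Conclusion.** The point holds. For one of the four targeted Aim 1 measures, the plan hypothesizes one difference and offers power for another without reconciling them, and the power it implies is not there for either: about 4% at 2 points and about 46% at 7, against about 9.9 points for 80%. This rests on the plan's SD of 15, 50 evaluable per group, pairwise comparisons at two-sided 0.016, and reading 80% across from the TST sentence. The conclusion at 2 points survives every variant tried. At 7 points, 80% is reached only under readings that contradict the stated design or α.

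Two stronger conclusions are not supported. A reader might infer that Aim 1 should rest on TST or REM instead. But TST has only about 52% power on its stated inputs, as does REM if 0.016 applies, and REM's 15 minutes does not match its pilot median difference (86 − 63 = 23). A reader might also infer that a null sleep-efficiency result would count against HT. No section makes this measure decisive alone; section 2.1 postulates improvement across several PSG variables.

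**What to change.** In the Power Analysis of 8.3.1:

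1. State one target difference for sleep efficiency and why it was chosen. If 2 points remains the hypothesis, say that the trial is not powered for it. If a larger value is the real target, replace the 2 and justify the new figure.
2. Correct the power statement: with SD 15, 50 per group and two-sided 0.016, power is 80% only for about 9.9 points, about 46% for 7 and about 4% for 2.
3. State that a non-significant sleep-efficiency result does not in itself rule out a 2-point effect, and that the estimate will be reported with its confidence interval.

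Keeping 7 points with its present wording is not a repair. This is a text change: no added subjects, no change to procedures, and no need to demote the endpoint. The cost is a less favourable stated figure for this measure.

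### The SDs behind the sleep power figures (TST 70 min, efficiency 15 points, WASO 50 min) have no stated source and are smaller than the pilot quartiles imply, clearly so for WASO

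*Combined protocol and SAP*

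**What the plan says.** Section 8.3.1, under Power Analysis, prints medians and quartiles from a 15-subject crossover pilot and introduces them as the data on the sleep variables of interest. It then gives three statements that rest on an SD:

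- TST: "we will need a sample size of 50 per group for 80% power to detect a difference of 35 minutes, standard deviation of 70", two-sided, at a type I error rate of 0.016.
- Sleep efficiency: with the same 50 per group, "we would be able to detect a difference of 7% with a standard deviation of 15". The alpha is given as "2-sided test and type I error rate of 0.016, to account for comparing HT to the 3 control groups". Power is not repeated in that sentence; I read it as the same 80%.
- WASO: 50 per group is said to be what a 25-minute gap needs, on these terms: "For WASO, with an assumed standard deviation of 50, a type 1 error rate of 0.016, a power of 80% and a 2-sided test".

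No source is given for 70, 15 or 50, and no step leads from the printed quartiles to them. The WASO SD is described as assumed. The total of 200 follows from these statements.

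**The concern.** Each SD is smaller than the spread in the table printed just above it. The comparison is like with like. Section 4.1.1 rejects a crossover and randomizes to four parallel groups, and Section 4.2 records one PSG night per subject. There is therefore no within-subject contrast and no baseline PSG to adjust for. The SD that matters is the spread between subjects on one night, which is what the pilot quartiles describe.

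These are Aim 1 primary measures. If the SDs are too small, the plan promises sensitivity that the trial does not have, and a null result could be read as evidence against effects it was unlikely to detect. Correcting only the power arithmetic while keeping 70, 15 and 50 would leave that problem in place.

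**Working it through.** **Inputs.** Section 8.3.1: 50 per group; two-sided alpha 0.016; differences 35 min, 7 points and 25 min; SDs 70, 15 and 50; pilot quartiles as in step 2.

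**Step 1. The plan's figure at its own SDs.** By the normal approximation, n per group = 2(z₀.₉₉₂ + z₀.₈₀)² / (d/SD)² = 2(2.409 + 0.842)² / (d/SD)².

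- TST and WASO: d/SD = 35/70 = 25/50 = 0.5, so n = 85 (86 by the t distribution).
- Efficiency: d/SD = 7/15 = 0.467, so n = 98 (99 by t).

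By the noncentral t, power with 50 per group is 52%, 46% and 52% for TST, efficiency and WASO. The stated 50 is not reproduced. A one-sided 0.05 test does give 50 for TST and WASO, but the plan says two-sided. This error is separate from the SD question and is the starting point for it.

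**Step 2. SDs implied by the pilot.** SD ≈ (Q3 − Q1)/1.349 for each night, pooled as the root mean square of the two nights.

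| Measure | HT night | Non-HT night | Pooled | Plan | Pooled/plan |
|---|---|---|---|---|---|
| TST (min) | (442 − 302)/1.349 = 103.8 | (396 − 287)/1.349 = 80.8 | 93.0 | 70 | 1.33 |
| Efficiency (points) | (90 − 61)/1.349 = 21.5 | (82 − 56)/1.349 = 19.3 | 20.4 | 15 | 1.36 |
| WASO (min) | (160 − 47)/1.349 = 83.8 | (181 − 82)/1.349 = 73.4 | 78.7 | 50 | 1.57 |

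All six values exceed the plan. REM minutes (pooled 34 against 30) is broadly in line and is not questioned here.

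**Step 3. Consequence at 50 per group, two-sided 0.016 (noncentral t).** The standardized difference detectable with 80% power is 0.660, which agrees with the 0.66 in Section 8.3.3.

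| Measure | Power, plan SD | Power, pooled pilot SD (range over nights) | Detectable, plan SD | Detectable, pooled pilot SD |
|---|---|---|---|---|
| TST, 35 min | 52% | 29% (23–39%) | 0.660 × 70 = 46 min | 0.660 × 93.0 = 61 min |
| Efficiency, 7 points | 46% | 24% (21–27%) | 0.660 × 15 = 9.9 points | 0.660 × 20.4 = 13.5 points |
| WASO, 25 min | 52% | 20% (17–23%) | 0.660 × 50 = 33 min | 0.660 × 78.7 = 52 min |

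**Step 4. Could chance explain the gap?** I simulated 15-subject pilots with normal data, the plan's SDs taken as true, and between-night correlation from 0 to 0.8. The table shows how often the pooled value is at least as large as the one observed. The answer depends on the quartile rule, which the plan does not state.

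| Measure | Interpolated quartiles | SAS default quartiles |
|---|---|---|
| TST | about 2–5% | about 13–16% |
| Efficiency | about 2–4% | about 10–13% |
| WASO | under 1% | about 2–3% |

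The small-sample correction depends on the same rule. Under the SAS default, IQR/1.349 overstates the SD by about 8% at n = 15, giving about 86, 19 and 73 (power 34%, 28% and 24%). A common small-sample divisor goes the other way and gives about 103, 22.5 and 87.

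**The case against.** The plan never says that its SDs came from the table, so this is an unsourced assumption rather than a sum done wrongly. That stands, and it is why citing another source would be an acceptable answer.

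The pilot is small, and the conversion assumes near-normal data. The printed quartiles are skewed: WASO on the non-HT night has median 85 with quartiles 82 and 181. A flat distribution would give pooled SDs of 72, 16 and 61, close to the plan for TST and efficiency but not for WASO. Section 8.1 names SAS, and under its default quartile rule the TST and efficiency gaps are within ordinary sampling error. So a reader might infer that all three SDs are refuted, but the documents support that only for WASO. Even the flat case leaves power at about 49%, 41% and 34%.

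A reader might also infer that the SDs alone double the detectable differences (61 against 35 min, for instance). That comparison includes the error in step 1. The SD gap contributes factors of 1.33, 1.36 and 1.57.

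The 10-child table in Section 1.1 gives pooled values of about 130, 23 and 113, in the same direction. The documents do not say whether its subjects overlap with the 15, so it should not be counted as independent confirmation. Both tables may also describe a population different from the elective-surgery patients aged 5 to 25 enrolled here.

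Covariates could reduce the residual SD, and the plan mentions age, gender and practitioner. To reach 70, 15 and 50 from the pooled values they would have to explain 1 − (70/93.0)² = 43%, 46% and 60% of the variance. The plan claims no such reduction, and Section 8.3.1 adds covariates in secondary analyses.

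**Conclusion.** The concern holds. The planning SDs are unsourced, and all three lie below the spread in the plan's own pilot table. The inconsistency is clear for WASO. For TST and efficiency it is consistent in direction but could be sampling error. At the pooled pilot SDs, power for the stated differences is about 29%, 24% and 20%, compared with about 52%, 46% and 52% at the stated SDs. No SD that the documents support delivers 80% for these three measures.

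This rests on IQR/1.349 as an approximation to the SD, a two-sample t-test with 50 evaluable subjects per group, two-sided alpha 0.016 and no variance reduction from covariates. The values 93, 20.4 and 79 are approximations within a range. The printed quartiles do not justify using them as fixed replacements.

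**What to change.** In Section 8.3.1, compute the single-night between-subject SDs of TST, sleep efficiency and WASO from the pilot raw data, which removes the dependence on quartile rule and distribution. Alternatively, cite the source of 70, 15 and 50 and explain why it overrides the printed table. Then restate the power, or the differences detectable with 80% power, that 50 per group delivers at two-sided 0.016, correct the arithmetic in the same pass, and show a range for uncertainty in the SD.

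The cost is a recalculation and a reworded paragraph. No extra patients are needed. The downside is that the stated figures become less favourable: on the printed quartiles, roughly 53–69 min for TST, 12.7–14.2 points for efficiency and 48–55 min for WASO (0.660 times the SD of each night).
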